6.3.2. Evaluation of Adverse Events or Laboratory Abnormalities

While specific monitoring, diagnostic testing, and supportive care measures must be instituted based on the clinical judgment of the investigator, investigators are encouraged to contact either the PTC Therapeutics medical monitor (or designee) to obtain guidance and to ascertain whether similar events are being seen at other investigator sites. The PTC Therapeutics medical monitor should be notified of any adverse event or laboratory abnormality that leads to dose interruption and should be apprised of ancillary laboratory or other diagnostic findings and the evolving data from any work-up of the initial abnormality. The PTC Therapeutics medical monitor may suggest review of the case with gastroenterology or nephrology consultants or with other experts (either at the site or retained by PTC Therapeutics).

Clinical evaluations for potential hepatic and renal toxicities may include the following:

- **Hepatic:** The medical history, hepatitis screening results, all clinical blood values (particularly serum bilirubin, GGT, AST, and ALT values), and all concomitant medications should be reviewed. Depending upon changes observed, the recommended diagnostic workup may include more frequent monitoring or further evaluations for viral hepatitis and immune disorders; tests for cholelithiasis; or abdominal ultrasound, computed tomography (CT), magnetic resonance imaging (MRI), or other imaging methods.
- **Renal:** The medical history, baseline ultrasound data, all clinical blood and urine renal values, serum electrolytes, medications, and potential pre- or post renal conditions should be reviewed. Depending upon the changes observed, recommended diagnostic workup may include further evaluations of blood or urine; tests of glomerular filtration rate (GFR), concentrating ability, or other renal functions; CT, MRI, or other imaging methods; and/or renal biopsy.

Laboratory evaluation for adrenal function (cortisol, renin and aldosterone) will be performed at screening to determine normal clinical function. The results of placebo-controlled clinical trials with ataluren in nmCF and nmDBMD showed no meaningful imbalances in adrenal laboratory assessments between the ataluren and placebo arms; therefore, regular monitoring of function is not warranted and will not be performed routinely during study participation. However, adrenal function (via these or other parameters) may be tested in patients with evidence of adrenal dysfunction as clinically indicated.

The incidence of new onset nephrolithiasis was similar in both the ataluren and placebo arm in the previous double-blind study (4.2% on ataluren vs 3.4% on placebo). All cases involving the diagnosis of urinary tract calculi should be reported as adverse events of special interest to the CRO Pharmacovigilance Unit (see Section 9.1.2). Once it has been documented that a patient has symptomatic nephrolithiasis, determining the type of stone and the possible presence of either biochemical abnormalities or underlying conditions that predispose to stone formation are essential for guiding therapy to prevent recurrent disease. Patients should be encouraged to retrieve stones they pass or have removed for analysis. Analysis of the stone is an essential part of the evaluation. All patients presenting with their first stone should undergo a focused history, radiologic imaging, and at least a limited laboratory evaluation. A complete metabolic evaluation, in addition to the basic laboratory testing, is indicated in all patients with multiple stones at first presentation, in patients with a strong family history of stones, and in individuals with active stone disease, which is defined as recurrent stone formation, enlargement of existing stones, or the recurrent passage of gravel. The purpose of the focused history is to identify stone risk factors, such as a family history of stone disease and certain dietary habits. Adverse dietary habits include:

- Low fluid intake or a high fluid loss (eg, from sweating or gastrointestinal losses), which leads to a lower urine output and, therefore, a higher concentration of lithogenic factors.
- Higher animal protein diet, which can lead to hypercalciuria, hyperuricosuria, hypocitraturia, and elevated urinary acid excretion.
- Higher salt diet, which increases urinary calcium excretion.
- Increased intake of higher oxalate-containing foods, particularly spinach (the exact contribution of dietary oxalate to urinary oxalate is controversial and likely varies considerably from person to person).
- Lower calcium intake, which acts by increasing the absorption and subsequent excretion of oxalate due to decreased calcium oxalate complex formation within the intestinal lumen [Curhan 1997, von Unruh 2004]. The effect on oxalate more than counterbalances the decrease in calcium absorption and excretion.
- Excessive vitamin C and D supplementation.
- Excessive sugar (fructose) intake, which may increase calcium and/or oxalate excretion.

Because the risk of nephrolithiasis is influenced by urine composition, which can be affected by certain diseases and patient habits, a thorough clinical history and analysis of urine composition should be completed. For calcium oxalate stones, urinary risk factors include hypercalciuria, hyperoxaluria, hypocitraturia, and dietary risk factors such as a low calcium intake, high oxalate intake, high animal protein intake, high sodium intake, or low fluid intake. The patient should be

evaluated for possible underlying causes of stone disease, including hypercalcemia, hypercalciuria, hyperuricosuria, hypocitraturia, hyperoxaluria, and urine volume.

6.3.3. Instructions for Resuming Study Drug Administration after an Interruption for Safety Concerns

In deciding whether to re-institute study drug after a dose interruption for any clinically significant safety concern, the investigator should consider factors such as the following:

- Type and severity of the adverse event or laboratory abnormality
- The potential causal relationship of study drug
- The patient's status in terms of CF and other health conditions
- The ability to monitor for recurrence of the event

For hepatic or renal events (refer to Table 2), the level of investigator certainty that an abnormality leading to drug interruption is drug-related should be considered strongly in deciding whether or not to re-institute study drug treatment. If the investigator considers the hepatic or renal event that led to study drug interruption to be probably related to study drug, restarting study drug is not advised. In this case, the patient should be discontinued from the study (see Sections 6.3.4 and 10). If the investigator considers the hepatic or renal event that prompted study drug interruption to be possibly related to study drug, the investigator should use best judgment in determining whether to restart study drug. If the hepatic or renal event is considered unrelated to study drug, re-institution of study drug is recommended.

If the investigator believes it is appropriate, after consultation with the PTC Therapeutics medical monitor, study drug may be re-initiated. If the event was determined to be unrelated to study drug, the treatment may be resumed at full dose. Otherwise, if the drug is resumed, it may be initially re-initiated at half of the original dose. If a patient cannot tolerate the full dose within 30 days of dosing re-initiation, then the patient is to be discontinued from study participation.

If after dose reduction, the patient experiences a recurrence of a previous abnormality that led to study drug dose interruption or experiences the new occurrence of an unacceptable adverse event or laboratory abnormality, the investigator should interrupt study drug and confer with the PTC Therapeutics medical monitor regarding the potential need to discontinue study drug permanently.

6.3.4. Instructions for Discontinuation of Study Drug Administration for Safety Concerns

If after appropriate consideration of study drug interruption/modification and consultation with the PTC Therapeutics medical monitor, it is not appropriate for a patient to continue with study treatment, then study drug should be permanently discontinued. After permanent discontinuation of study drug for a safety concern, and if the initial event was reported as a SAE, then the SAE portion of the CRF should be updated. In the case of a treatment discontinuation due to an event that is not an SAE, the PTC Therapeutics medical monitor should be notified (see Section 9). In addition, details regarding the reasons for discontinuation and the adverse events leading to the discontinuation should be recorded in the source documents and in the appropriate CRF. The End of Treatment Visit CRF should be completed and appropriate follow-up (at ~4 weeks as per protocol or until recovery from or stabilization of the adverse event, whichever comes last) should be instituted.

7. CONCOMITANT AND SUPPORTIVE THERAPY

7.1. Concomitant Medications

Other than the study drug, any treatments (including prescription and non-prescription drugs, health foods, herbal remedies, self-prescribed drugs, street drug, tobacco products, or alcohol) taken by a patient during the screening period, during study drug administration, and for 4 weeks after discontinuation of study drug are considered concomitant medications. Information regarding all concomitant medications will be collected and documented in the concomitant medication page of the CRF.

7.1.1. Therapy/Prophylaxis for CF-Related Conditions

Study patients may receive existing therapy/prophylaxis for treatment of CF or CF-related conditions. To the extent possible, changes in drug regimens should be avoided because this may confound interpretation of study results. The decision to authorize the use of any drug other than ataluren should take into account patient safety, the medical need, the potential for drug interactions, the possibility for masking symptoms of a more relevant underlying event, and whether use of a concomitant medication will compromise the outcome or integrity of the study.

For patients who are not on a particular type of CF-specific therapy/prophylaxis (eg, dornase alfa, hypertonic saline oral azithromycin or ibuprofen), initiation of such therapy/prophylaxis during ataluren treatment is discouraged unless there is a strong medical need. For patients who are on CF-specific therapy/prophylaxis at baseline, a stable regimen should be maintained during the 96 weeks of ataluren treatment. Adjustments in dosage or type of drug are permitted to avoid symptoms, but attempts should be made to avoid entirely removing or substituting CF treatments. However, patients who do require initiation, interruption, dose modification, or substitution of CF treatment may remain on ataluren therapy.

7.1.2. Therapy for CF Pulmonary Exacerbations or Other CF Complications

Patients should receive appropriate antibiotic or other therapy for CF pulmonary exacerbations or other CF-related complications (eg, DIOS) consistent with local best practices and guidelines. For patients requiring systemic antibiotic therapy, IV aminoglycosides may be used when medically necessary. However, given ataluren's ribosomal mechanism of action, and the possibility of aminoglycosides exhibiting a confounding effect upon study results, investigators should substitute other antibiotics for systemic aminoglycosides in patients who require treatment for serious infections whenever possible. For such severe infections, consideration should be given to use of appropriate alternative anti-pseudomonal agents including macrolide and glycopeptide antibiotics. Patients requiring IV therapy with an aminoglycoside or glycopeptide antibiotic (eg, vancomycin), should be closely monitored in an appropriate setting. Particular caution should be used for patients with a previous history of clinically significant creatinine elevations. Based on the increased incidence of creatinine elevation in patients treated with IV aminoglycosides and/or vancomycin, concomitant use of these medications with ataluren is contraindicated. If nephrotoxic antibiotics (eg, tobramycin or vancomycin) are administered, ataluren treatment must be interrupted for the duration of IV antibiotic treatment. In patients receiving any type of potentially nephrotoxic antibiotics, antibiotic drug levels, and renal function should be closely monitored. Creatinine and BUN should be measured prior to initiating IV aminoglycosides or other potentially nephrotoxic therapy, and at least twice a week during the course of such antibiotic treatment. The antibiotic trough level, creatinine and BUN

should be measured within 24 to 48 hours of administration of the first antibiotic dose, and further antibiotic dosing should be based on these results. Trough levels should also be measured at intervals during the course of antibiotic treatment.

Additionally, patients should be adequately hydrated prior to receiving potentially nephrotoxic IV antibiotics, and hydration status should be carefully monitored throughout the administration of these agents. Investigators should be particularly vigilant with patients who are experiencing nausea, vomiting, diarrhea, fever, or who have laboratory evidence of dehydration. Treatment with ataluren may be resumed no earlier than 2 days after administration of nephrotoxic antibiotics has ceased.

In patients receiving non-nephrotoxic systemic antibiotics, creatinine and BUN should be measured at least once per week during the course of treatment for a pulmonary exacerbation.

It should be emphasized to patients/caregivers that they must always carry with them the existing 24-hour emergency card for the study to enable non-study physicians providing care at local hospitals or emergency facilities to communicate with the investigational site to ensure that appropriate supportive care and monitoring recommendations are followed.

Information regarding the types and durations of intervention for CF pulmonary exacerbations should be recorded on source documents and will be specifically collected in the CRFs in support of both the safety and efficacy analyses of the study.

Chronic use of inhaled aminoglycosides (eg, tobramycin and gentamicin) is prohibited during study participation based on the results of Study 009, although short regimens (up to 3 months total) are permitted for eradication of newly acquired *Pseudomonas aeruginosa* infection but must be completed during the first 12 weeks of treatment. However, eradication protocols with alternative antibiotics should be considered. Patients requiring *Pseudomonas aeruginosa* eradication protocols including inhaled tobramycin in the last 12 weeks of the study must be withdrawn from study participation. Start and stop dates for all inhaled antibiotics used during the study must be captured in the eCRF. If there is a time gap between the end of the pivotal 021 study and this 021 extension of longer than one month, the participating subjects must have been off inhaled tobramycin at least 4 weeks prior to screening into 021e.

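### Protocol 7.1.2 suggests glycopeptides in place of systemic aminoglycosides, but the only one it names, IV vancomycin, is contraindicated with ataluren and requires the same interruption

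*Protocol*

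**What the plan says.** Protocol 7.1.2 allows IV aminoglycosides when medically necessary but asks investigators to use other antibiotics where they can. The reasons given are ataluren's ribosomal mechanism and "the possibility of aminoglycosides exhibiting a confounding effect upon study results". For severe infections it then says that "consideration should be given to use of appropriate alternative anti-pseudomonal agents including macrolide and glycopeptide antibiotics".

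The rest of the section treats the named glycopeptide like an aminoglycoside:

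- Close supervision: "Patients requiring IV therapy with an aminoglycoside or glycopeptide antibiotic (eg, vancomycin), should be closely monitored in an appropriate setting".
- Contraindication, with its reason: "creatinine elevation in patients treated with IV aminoglycosides and/or vancomycin, concomitant use of these medications with ataluren is contraindicated".
- Interruption: "If nephrotoxic antibiotics (eg, tobramycin or vancomycin) are administered, ataluren treatment must be interrupted for the duration of IV antibiotic treatment".
- Restart: "Treatment with ataluren may be resumed no earlier than 2 days after administration of nephrotoxic antibiotics has ceased".
- Renal tests: "Creatinine and BUN should be measured prior to initiating IV aminoglycosides or other potentially nephrotoxic therapy, and at least twice a week" during the course.

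The section also recognises a lighter category: "In patients receiving non-nephrotoxic systemic antibiotics, creatinine and BUN should be measured at least once per week". It sets no interruption rule for that category.

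Protocol 14.2.10 repeats the prohibition on combining ataluren with nephrotoxic systemic antibiotics, giving aminoglycosides and vancomycin as examples. It leaves inhaled vancomycin unrestricted.

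**The concern.** The list of alternatives includes a class whose only named member is on the protocol's own list of renal hazards. An investigator who takes the suggestion and gives IV vancomycin must stop ataluren, wait at least 2 days after the last antibiotic dose, and test renal function on the heavier schedule. An aminoglycoside would have required the same. The sentence states no preference for agents that avoid these consequences, although the section goes on to describe such a category.

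What is at stake is avoidable time off ataluren, and advice that pulls against the contraindication stated a few lines later. The setting is not remote. Protocol 14.2.4 reports 7 serious renal events in Study 009, all in the ataluren arm and all associated with nephrotoxic systemic antibiotics, which were generally given for pulmonary exacerbations. Section 7.1.2 governs that same situation.

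**Working it through.** The plan gives no figure to reproduce. The first step sets the rules side by side; the second puts a size on them.

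**Step 1: rules by type of systemic antibiotic (Protocol 7.1.2)**

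| | IV aminoglycoside | IV vancomycin | Non-nephrotoxic agent |
|---|---|---|---|
| Combined with ataluren | Contraindicated | Contraindicated | Not contraindicated by this section |
| Ataluren during the course | Interrupted | Interrupted | No interruption required |
| Earliest restart | 2 days after the antibiotic ends | 2 days after the antibiotic ends | Not applicable |
| Creatinine and BUN | Before start, then at least twice weekly | Before start, then at least twice weekly | At least weekly |
| Aminoglycoside interference | Possible | Avoided | Avoided |

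The first two columns differ only in the last row, which is the reason the protocol gives for substitution. Inhaled vancomycin does not resolve the conflict, because the sentence concerns substitutes for systemic aminoglycosides.

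**Step 2: days off ataluren**

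Inputs:

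- Planned treatment is 96 weeks (Protocol 6.2.1): 96 × 7 = 672 days.
- The interval between visits is 12 weeks (Protocol Table 3): 12 × 7 = 84 days.
- The restart delay is at least 2 days (Protocol 7.1.2).
- IV course length is not in the documents. Values of 10, 14 and 21 days are assumed.

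Formula: minimum days off ataluren = course length + 2.

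| Assumed IV course | Days off | Share of 672 days | Share of 84 days |
|---|---|---|---|
| 10 days | 10 + 2 = 12 | 12/672 = 1.8% | 12/84 = 14.3% |
| 14 days | 14 + 2 = 16 | 16/672 = 2.4% | 16/84 = 19.0% |
| 21 days | 21 + 2 = 23 | 23/672 = 3.4% | 23/84 = 27.4% |

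- IV vancomycin minus aminoglycoside, equal course: 12 − 12 = 16 − 16 = 23 − 23 = 0 days.
- IV vancomycin minus non-nephrotoxic agent: 12, 16 or 23 days.

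**Step 3: minimum creatinine and BUN tests**

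For a nephrotoxic agent, count one test before the start and two per week, with the 24-to-48-hour test taken as one of the weekly tests. For a non-nephrotoxic agent, count one per week.

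- 14 days: 1 + 4 = 5 against 2.
- 21 days: 1 + 6 = 7 against 3.

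**The case against.** The strongest reply is that the two pieces of advice serve different purposes. Substitution is recommended to avoid ribosomal confounding, and Protocol 14.2.10 gives the rationale: aminoglycosides are theorized to interfere with ataluren's mechanism. IV vancomycin meets that aim. The renal rule is separate and bars only the combination with ataluren. An investigator reading 7.1.2 meets the monitoring, contraindication and interruption rules straight after the suggestion, and can comply with all of them by stopping ataluren. This stands. It shows that no safeguard is missing and that no instruction is impossible to follow. It does not explain why the list includes a drug that forces ataluren off without stating a preference for agents that do not.

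A reader might go further in three ways that the documents do not support.

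- *That IV vancomycin brings no renal advantage over an aminoglycoside.* The documents do not compare the two given alone. Protocol 1 ties the Grade 3-4 creatinine elevations to nephrotoxic antibiotics combined with ataluren, and interruption removes that combination. Protocol 14.2.4 says that prohibiting concomitant use dealt with the problem. Protocol 15.3 links the Grade 3-4 elevations to systemic aminoglycosides, and the number of the 7 serious events that involved vancomycin is not given.
- *That a non-nephrotoxic agent would always do the job better.* Section 7.1.2 names no agent as non-nephrotoxic and leaves the choice to local practice. Other agents can carry their own cautions: Protocol 7.1.5 advises care with ciprofloxacin because its concentration may rise. Hence the qualifier *where clinically suitable*.
- *That interruption should apply to every glycopeptide.* The rule in 7.1.2 covers nephrotoxic antibiotics, with vancomycin as an example. Nothing in the documents classes all glycopeptides as nephrotoxic.

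**Conclusion.** The inconsistency is real and minor. Section 7.1.2 offers a class of substitutes whose only named member, given IV, carries the same contraindication, interruption, restart delay and monitoring as the drugs to be replaced. The recommendation is poorly aligned with the section's own rules, but those rules are present and workable.

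Per course, IV vancomycin saves 0 ataluren days against an aminoglycoside of equal length. It costs at least 12 to 23 days against a non-nephrotoxic agent. That range rests on the assumed 10 to 21 day course, on restart at the earliest permitted time, and on a suitable non-nephrotoxic agent being available. The documents give no frequency of IV vancomycin use, so nothing is claimed about the study as a whole.

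**What to change.** Change one sentence of Protocol 7.1.2, the one recommending alternatives for severe infections: insert *preferably non-nephrotoxic* after *agents* and delete *and glycopeptide*. Macrolides stay as the named class, and the list stays open. Leave the monitoring, interruption and restart wording as it is. IV vancomycin remains available when medically necessary, with ataluren stopped under the existing rules.

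The cost is a one-sentence amendment, a letter to sites and one fewer named alternative. Visits, data collection and analysis are unaffected. SAP 2.1 records that the study was terminated early, so the benefit lies mainly with any later protocol that reuses this text.

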In the Phase 3 clinical trial (Study 009), serious adverse events related to renal dysfunction, which occurred only in the ataluren arm, included 3 patients with acute renal failure, 3 patients with renal failure, and 1 patient with hypercreatininemia. These events were characterized by elevated creatinine (Grade 1 to Grade 4), which resolved over days to weeks. Only 1 patient experienced symptoms of renal dysfunction (transient oliguria). All 7 events were associated with concomitant systemic treatment with potentially nephrotoxic antibiotics (eg, aminoglycosides, vancomycin) that were generally administered as treatment for pulmonary exacerbations. No patient required dialysis. One patient was unblinded and 1 patient chose not to continue study drug treatment; the remaining 5 of 7 patients restarted study medication and continued study participation without recurrent creatinine elevations. This issue was recognized during the conduct of the study and changes were made in the protocol (eg, prohibition of concomitant use of potentially nephrotoxic agents), which successfully addressed the issue.

Non-serious creatinine elevations occurred predominantly in the ataluren arm and were transient, generally mild, and resolved with or without interruption of study medication. The incidence of treatment emergent nephrolithiasis was similar in the ataluren and placebo groups.

Non-serious episodes of creatinine elevation in Study 009 occurred predominantly in the ataluren arm and were transient, generally mild, and resolved with or without interruption of study medication. However, there was no clinically meaningful difference in creatinine between the ataluren and placebo arms at Week 48, indicating that there was no cumulative effect of these transient elevations on renal function. The incidence of treatment-emergent nephrolithiasis was similar in the ataluren and placebo groups.

The renal monitoring program included in this protocol considers nonclinical and clinical findings with ataluren and past experience with known nephrotoxicants. Concomitant use of potentially nephrotoxic antibiotics with ataluren is prohibited. A focus is placed on well-established clinical indictors of renal dysfunction for making diagnostic decisions and prompting treatment interruptions/ modifications in individual patients. The rationale for each of the decision-making parameters is discussed below.

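### Section 7.1.2 lets ataluren resume 2 days after nephrotoxic IV antibiotics with no creatinine or BUN required after the last antibiotic dose

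*Protocol*

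**What the plan says.** Section 7.1.2 of the protocol contraindicates ataluren together with IV aminoglycosides or vancomycin. If such drugs are needed, "ataluren treatment must be interrupted for the duration of IV antibiotic treatment". Creatinine and BUN are to be measured before the course starts, again 24 to 48 hours after the first antibiotic dose, "and at least twice a week during the course of such antibiotic treatment". Renal function is also to be watched closely in patients receiving these drugs.

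For the restart, the section gives one condition: "Treatment with ataluren may be resumed no earlier than 2 days after administration of nephrotoxic antibiotics has ceased". It names no laboratory test, no threshold and no consultation.

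Table 2 (section 6.3.1) requires ataluren to be stopped for a confirmed creatinine above the ULN for age or a confirmed BUN of at least 1.5 x ULN. The stop is immediate at creatinine of at least 1.5 x ULN or BUN of at least 3.0 x ULN. These stops apply whatever the cause.

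Section 14.2.4 describes the serious renal events in Study 009, all in the ataluren arm and all with potentially nephrotoxic antibiotics: "These events were characterized by elevated creatinine (Grade 1 to Grade 4), which resolved over days to weeks". It says that the protocol changes made during that study, such as prohibiting concomitant nephrotoxic agents, were ones "which successfully addressed the issue".

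**The concern.** Creatinine elevation around nephrotoxic antibiotics is the main renal risk that the protocol describes, and the hold in 7.1.2 is the response to it. Yet the hold ends on elapsed time alone. Every required creatinine and BUN falls before or during the antibiotic course, so a rise that appears or persists at the end of the course need not be seen before ataluren is given again.

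This sits badly beside Table 2. One part of the protocol stops drug for a confirmed creatinine just above the ULN for age. Another allows drug to restart, after exposure to a known nephrotoxin, without knowing whether creatinine is above that limit. At stake is individual patient safety in a study whose primary objective is long-term safety.

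**Working it through.** The plan gives no figure to reproduce. The check lines up the required tests and works out two time gaps.

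**Inputs**
- Minimum wait before restart: 2 days (7.1.2).
- Testing during the course: at least two draws a week (7.1.2). Spacing within the week is not stated, so it is varied below.
- Scheduled biochemistry: every 12 weeks, each visit ±7 days (Table 3).
- Study 009 serious renal events: 3 acute renal failure, 3 renal failure, 1 hypercreatininemia (14.2.4).

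**Step 1. Required creatinine and BUN around an antibiotic course**

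| Period | Required by 7.1.2 or Table 3 |
|---|---|
| Before the course | Yes |
| 24 to 48 hours after first dose | Yes |
| Rest of the course | At least two a week |
| Last antibiotic dose to restart | None |
| After restart | None until the next scheduled visit |

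**Step 2. Age of the last required value at the earliest restart**

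Age = (last antibiotic day − day of last draw) + 2.
- Draw on the last antibiotic day: 0 + 2 = 2 days.
- Draws evenly spaced, the longest gap: 7/2 + 2 = 5.5 days.
- Both draws on days 1 and 2 of a final full week: (7 − 2) + 2 = 7 days.

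In every case the sample was taken during the course. The third case assumes a complete final week. A loose reading of the twice-weekly rule over an incomplete last week would allow an older value, which is not counted here.

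**Step 3. Time to the next scheduled biochemistry**
- Nominal interval between visits: 12 x 7 = 84 days.
- Later visit at the end of its window: 84 + 7 = 91 days.
- Earlier visit 7 days early and later visit 7 days late: 84 + 7 + 7 = 98 days.

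The 98 days is the longest interval between visits. It is a ceiling on the wait after a restart, not a typical wait.

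**Step 4. What would catch a raised value at restart**
- Table 2 acts on a measured value.
- Section 9.1.2 makes creatinine above the ULN for age and BUN above 1.5 x ULN adverse events of special interest, reportable within 24 hours. That too needs a measured value.
- Medical-monitor consultation before restart is in 6.3.3, which covers interruptions for a safety concern. The 7.1.2 hold is triggered by a concomitant drug, and 7.1.2 does not itself ask for consultation.

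None of these creates a measurement between the last antibiotic dose and the restart.

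**Step 5. What Study 009 adds**

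Events: 3 + 3 + 1 = 7. One patient was unblinded and one chose not to continue, leaving 7 − 1 − 1 = 5 who restarted, without recurrent creatinine elevation. Section 14.2.4 does not give their creatinine at restart.

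**The case against.** The strongest reply is that the documents show no harm from restarting. The only restart experience reported is favourable: 5 of 7 patients resumed in Study 009 without recurrence. The 2 days is a floor, resumption is optional, and an investigator may test at any time. A patient stepped down to a non-nephrotoxic systemic antibiotic for an exacerbation would have creatinine and BUN at least weekly under 7.1.2. Adverse events are followed to resolution or stability (9.7). All of this stands and limits the size of the point. None of it requires a value after the last nephrotoxic dose to be seen before ataluren is resumed.

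Three stronger readings are tempting and are not supported.

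- A reader might infer that a 2-day restart will usually precede recovery. Assumed recovery times of 7, 14 or 21 days from the last antibiotic day would give 7 − 2 = 5, 14 − 2 = 12 or 21 − 2 = 19 days of overlap. Those durations are assumptions. The recovery described in 14.2.4 was seen when ataluren and the antibiotics were given together, which this protocol bars. The documents give no time course for courses with ataluren held.
- A reader might infer that the protocol allows dosing at a known stop-range value. It does not: Table 2 applies throughout, so the exposure is to an unmeasured value.
- A reader might extend the criticism to 6.3.3, where "If the hepatic or renal event is considered unrelated to study drug, re-institution of study drug is recommended" and no recovery value is demanded after a Table 2 stop. There, however, a work-up is already called for, the medical monitor should be told of "the evolving data from any work-up of the initial abnormality", and only "after consultation with the PTC Therapeutics medical monitor, study drug may be re-initiated". Restart is not advised after a probably related hepatic or renal event, half dose is available when the event is not judged unrelated, and 14.2.8 asks for flexibility. Numeric restart limits there, hepatic ones included, are a judgment trade-off, and the documents give no evidence of harm to settle it.

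**Conclusion.** The point holds for 7.1.2 only. A site that follows the section exactly can restart ataluren when the last required creatinine and BUN are about 2 to 7 days old and were drawn during the course. The next scheduled test may be about 12 weeks off. A stop-range value could go undetected in that interval.

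The 2-to-7-day range rests on restart at the first permitted moment, the draw spacings set out above and no testing beyond what is required. How often a patient would be restarted at a raised value cannot be estimated from the documents. This is a worthwhile safety correction, not evidence that patients were harmed. It is relevant only while patients are being dosed: SAP section 2.1 records early termination on 2 March 2017, with ongoing subjects to be discontinued.

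**What to change.** Change 7.1.2 only. Keep the 2-day minimum and add a creatinine and BUN, local laboratory acceptable, that is:
- drawn at least 2 days after the last nephrotoxic antibiotic dose;
- drawn within about 24 hours before resumption;
- reviewed before ataluren is given.

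Resume if creatinine is at or below the ULN for age and BUN is below 1.5 x ULN. Otherwise keep ataluren on hold and manage the patient under Table 2 and 6.3.3 with the medical monitor. The timing matters: a sample taken hours after the last antibiotic dose could itself be about 2 days old at restart. The limits are the protocol's own Table 2 limits, and the two tests are those 7.1.2 already uses. Cystatin C, also a Table 2 parameter, is not covered.

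The cost is one blood draw per nephrotoxic antibiotic course, a longer hold in patients who recover slowly, and a wording change in one protocol section. No SAP change is needed.
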